#### 1.2.4 Summary of risks and potential benefits

This clinical trial is being performed to evaluate avelumab for RRP. Only patients with a substantial disease burden (Derkey anatomic score of 10 or greater) that requires repeated endoscopic interventions (two or more procedures in the last 12 months) will be eligible for treatment. While the vast majority of patients with RRP experience an acceptable level of disease control with infrequent surgical debulking, a small subset of patients have very aggressive disease that requires frequent operative intervention, carries the risk of airway obstruction and the need for a tracheostomy, and affects their voice and breathing to a degree that negatively impacts their quality of life. The inclusion criteria for this study captures these 5-10% of patients most severely affected. Patients with disease that has not met this level of severity will not be subjected to the risks of treatment. The primary protocol risks are the toxicities of avelumab. There may be additional risks of treatment that are specific to RRP such as swelling or progression of papillomas that may lead to worsening symptoms. In addition, there are risks from the general anesthesia and procedures to stage and monitor the disease. General anesthesia will be employed during an initial evaluation to stage the disease, confirm the diagnosis, and debulk papillomas that pose an undue safety risk. It will be used again two weeks after the initiation of treatment at which time the airway will be assessed for safety. A final procedure under anesthesia will be performed at the completion of treatment to remove residual papillomas if they are present. Rare but serious complications can occur with general anesthesia including cardiopulmonary compromise, stroke, and death. In this protocol they are offset substantially by the important safety information related to airway patency, extent of disease, and in some cases surgical removal of disease that is gained by these procedures.

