#### **3.3.1 Prior to each dose within 3 days of drug administration**

- Targeted physical examination if clinically indicated which may include clinic-based flexible nasopharyngolaryngoscopy and/or tracheoscopy with assignment of a Derkay score if the Derkay score is being used as the primary response assessment
- Vital signs and oxygen saturation at rest and after exertion
- Assess for symptoms of myocarditis (chest pain, shortness of breath, swelling of ankles or feet)
- Pregnancy test in women of childbearing potential

- CBC w/differential, LFTs (ALT, AST, total bilirubin, alkaline phosphatase), BUN or serum urea level, creatinine, Ca, Mg, Na, K, Cl, LDH, glucose, amylase, lipase, TSH with reflexive Free T4, Free T3
  - TBNK
  - Adverse events assessment
  - Research blood:
    - 6 Cell Preparation Tubes (CPT) (48 mL) will be collected for immunological testing and processed as described in section 4.1.1. Attention [name], [name] contact [contact].
    - 1 Serum Separator Tubes (SST) (8 mL) will be obtained for serum collection and processed as described in section 4.1.1 . Attention [name], [name] contact [contact].
  - Review of concomitant medications
  - Voice Handicap Index-10 assessment questionnaire
- 3.3.2 Additional studies at a single time point two weeks after the first dose of avelumab
- Leukapheresis (see Section 4.1.1)
  - Exam under anesthesia (sedation or general anesthesia) including rigid and/or flexible endoscopy with biopsies to assess disease response, clinical signs of inflammation or airway compromise, and to obtain biopsies for research.
- 3.3.3 Every 6 week (3 cycles) (+/- 7 days) response assessment (performed at 6 and 12 weeks after first dose of avelumab)
- Interval targeted history and physical.
  - Clinic-based flexible nasopharyngolaryngoscopy and/or tracheoscopy. This will include standard bright light endoscopy and videostroboscopy, and assignment of a Derkay score. This endoscopic examination combined with radiographic examination (if radiographically measurable disease is present) will be used to determine response to treatment.
  - Voice Handicap Index-10 assessment questionnaire, see Section 12.2.
  - Imaging studies if imaging is used for response assessment.
- 3.3.4 Every 1 week between on-site assessments

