#### 5.1.3 Collection of Adverse Events following surgery/procedure

Grade 1 or 2 adverse events that are clearly attributable to surgery/procedure will not be recorded.

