#### **7.1.2 Serious Adverse Event (SAE)**

An adverse event or suspected adverse reaction is considered serious if in the view of the investigator or the sponsor, it results in any of the following:

- Death,
- A life-threatening adverse event (see section 7.1.3)
- Inpatient hospitalization or prolongation of existing hospitalization
  - A hospitalization/admission that is pre-planned (i.e., elective or scheduled surgery arranged prior to the start of the study), a planned hospitalization for pre-existing condition, or a procedure required by the protocol, without a serious deterioration in health, is not considered a serious adverse event.
  - A hospitalization/admission that is solely driven by non-medical reasons (e.g., hospitalization for patient or subject convenience) is not considered a serious adverse event.
  - Emergency room visits or stays in observation units that do not result in admission to the hospital would not be considered a serious adverse event. The reason for seeking medical care should be evaluated for meeting one of the other serious criteria.
- Persistent or significant incapacity or substantial disruption of the ability to conduct normal life functions
- A congenital anomaly/birth defect
- Important medical events that may not result in death, be life-threatening, or require hospitalization may be considered a serious adverse drug experience when, based upon

appropriate medical judgment, they may jeopardize the patient or subject and may require medical or surgical intervention to prevent one of the outcomes listed in this definition.

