## 7.2 ASSESSMENT OF SAFETY EVENTS

AE information collected will include event description, date of onset, assessment of severity and relationship to study product and alternate etiology (if not related to study product), date of resolution of the event, seriousness and outcome. The assessment of severity and relationship to the study product will be done only by those with the training and authority to make a diagnosis and listed on the Form FDA 1572 as the site principal investigator or sub-investigator. AEs occurring during the collection and reporting period will be documented appropriately regardless of relationship. AEs will be followed through resolution.

SAEs will be:

- Assessed for severity and relationship to study product and alternate etiology (if not related to study product) by a licensed study physician listed on the Form FDA 1572 as the site principal investigator or sub-investigator.
- Recorded on the appropriate SAE report form, the medical record and captured in the clinical database.

- Followed through resolution by a licensed study physician listed on the Form FDA 1572 as the site principal investigator or sub-investigator.

For timeframe of recording adverse events, please refer to section **6.1**. All serious adverse events recorded from the time of first investigational product administration must be reported to the sponsor.

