### **7.3 REPORTING OF SERIOUS ADVERSE EVENTS**

Any AE that meets protocol-defined serious criteria or meets the definition of Adverse Event of Special Interest that require expedited reporting must be submitted immediately (within 24 hours of awareness) to OSRO Safety using the CCR SAE report form.

All SAE reporting must include the elements described in section **7.2**.

SAE reports will be submitted to the Center for Cancer Research (CCR) at: [[contact]](mailto:[contact]) and to the CCR PI and study coordinator. CCR SAE report form and instructions can be found at:

<https://ccrod.cancer.gov/confluence/pages/viewpage.action?pageId=157942842>

Following the assessment of the SAE by OSRO, other supporting documentation of the event may be requested by the OSRO Safety and should be provided as soon as possible.

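### Section 5.1.3 excludes low-grade procedural adverse events without exempting serious ones, which conflicts with sections 7.2 and 7.3 and leaves some post-dose airway events with no entry to review

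*Combined protocol and SAP*

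**What the plan says.** **The exclusion.** Section 5.1.3: "Grade 1 or 2 adverse events that are clearly attributable to surgery/procedure will not be recorded". The filter has two parts, CTCAE grade and clear attribution to a procedure. It does not mention seriousness, body site or timing relative to avelumab.

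**The general rule.** Section 7.2: "AEs occurring during the collection and reporting period will be documented appropriately regardless of relationship". The same section lists the data to be collected for each event, including another cause when the study drug is not held responsible.

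**The rules for serious events.** Section 7.2 says SAEs will be "Recorded on the appropriate SAE report form, the medical record and captured in the clinical database". It adds: "All serious adverse events recorded from the time of first investigational product administration must be reported to the sponsor". Section 7.3 applies the 24-hour submission rule to "Any AE that meets protocol-defined serious criteria", and section 7.4.2 sends SAEs to the manufacturer's parent company on the same timescale. None of these sets a minimum grade.

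**What makes an event serious.** Section 7.1.2 defines seriousness by outcome, one such outcome being "Inpatient hospitalization or prolongation of existing hospitalization". Severity is a separate matter, graded by CTCAE under section 7.1.4.

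**The disease-specific risk.** Section 1.2.4: "There may be additional risks of treatment that are specific to RRP such as swelling or progression of papillomas that may lead to worsening symptoms". The week 2 EUA in section 3.3.2 is done "to assess disease response, clinical signs of inflammation or airway compromise, and to obtain biopsies for research".

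**The concern.** There are two problems.

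First, a rule that filters on grade is applied to events whose reporting status does not depend on grade. A Grade 1 or 2 event after a procedure can be serious, for example if it leads to an unplanned admission. Sections 7.2 and 7.3 then say to record and submit it, and section 5.1.3 says not to record it. Site staff have no rule of precedence.

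Second, the protocol puts airway procedures with biopsies between and after avelumab doses, in the tissue where it expects a drug-specific reaction. Deciding whether mild edema or stridor came from the instrument or from the drug is a clinical judgment. Section 5.1.3 does not say how clear attribution is established or by whom, and once the event is judged procedural no adverse event entry remains. At stake are the completeness of the SAE data and the chance to re-examine low-grade airway attributions, including at the safety review after the first cohort (section 3.7.2).

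**Working it through.** The plan states no figure on this point. The check is a comparison of text, followed by a count of the procedures exposed to the rule.

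**1. The rules applied to one case.** Take a Grade 2 bleed after the week 2 EUA, clearly procedural, with an unplanned admission.

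| Section | Test applied | Instruction |
|---|---|---|
| 5.1.3 | Grade 1-2 and clearly procedural | Do not record |
| 7.2, general | Within the collection period | Document, whatever the cause |
| 7.1.2 | Outcome, here an admission | Can be serious |
| 7.2, SAEs | Serious | SAE form, medical record and database |
| 7.3 | Serious | Submit within 24 hours |

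Section 7.1.2 exempts admissions planned for a protocol procedure if health has not seriously deteriorated. It does not clearly exempt an unplanned admission for a complication.

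**2. Whether the text settles precedence.** Sections 5.1.3 and 7.2 do not refer to each other. For the recording timeframe, 7.2 points to section 6.1, which only cites an external policy for definitions. The sponsor-reporting sentence in 7.2 speaks of SAEs that have been recorded, so it does not expressly override 5.1.3. Section 7.3 has no such condition and so supports reporting. The conflict over recording stays open.

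**3. Post-dose EUAs exposed to the rule.**
- EUAs per patient after dosing: weeks 2 and 6 for everyone, and week 12 for partial responders who continue (section 3.3.5). That is 2 to 3. The baseline EUA is left out because it precedes avelumab.
- Patients: 37 evaluable, accrual ceiling 40 (section 9).
- Count: 37 × 2 = 74 to 40 × 3 = 120.

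The upper end requires every patient to continue as a partial responder. EUAs may also be cancelled (section 3.1.1). If accrual ends at the 12 patients of stage 1, the count is 12 × 2 = 24 to 12 × 3 = 36.

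**4. Illustration only.** The documents give no rate of low-grade events leading to admission. Suppose q is 0.5%, 1% or 2% per EUA, with independence between EUAs. The chance of at least one such event in n procedures is 1 − (1 − q)^n.

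| q | n = 74 | n = 120 |
|---|---|---|
| 0.5% | 1 − 0.995^74 = 31% | 1 − 0.995^120 = 45% |
| 1% | 1 − 0.99^74 = 52% | 1 − 0.99^120 = 70% |
| 2% | 1 − 0.98^74 = 78% | 1 − 0.98^120 = 91% |

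These are chances that the contradictory instructions are met at least once. They are not chances that an SAE is lost.

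**5. Airway events.** The first on-treatment EUA falls 9 to 17 days after dose 1 and before dose 2 (section 3.5), so drug and procedural causes can overlap in time and site. If the investigator finds the cause clearly procedural, 5.1.3 leaves no adverse event entry. Section 5.1.1 records only medications given for drug-related events, so treatment of the episode would not appear in the database through that route either.

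**The case against.** The strongest reply is that sensible staff would apply these sections together without difficulty. Much of it stands.

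- **SAEs.** A reader might infer that 5.1.3 takes low-grade SAEs out of reporting. The documents do not say so. Sections 7.2, 7.3 and 7.4.2 independently require SAEs to be recorded or reported with no grade limit. An SAE is lost only if staff treat 5.1.3 as controlling. The set is also narrow: 7.1.2 removes planned procedural admissions, and emergency or observation stays without admission.
- **Airway events.** A reader might infer that every mild event after an EUA disappears and the swelling signal with it. That too goes beyond the text. Only clearly procedural events are excluded, so one with a plausible avelumab cause stays recordable. Swelling seen at the start of the week 2 EUA cannot have been caused by that EUA. Endoscopy, Derkay scores, weekly symptom calls and the symptom criterion for progression (section 5.2.3.3) capture part of the signal, and monitoring checks data against source documents (section 8).
- **Trial decisions.** The event-based stopping triggers in section 3.7.1 need a treatment-related death or unexpected SAEs of Grade 3 or higher, so Grade 1-2 events cannot set them off. The trial is single-arm, so no safety comparison with debulking is distorted.
- **Noise.** Leaving out routine biopsy soreness or minor bleeding is a reasonable aim, and recording more would add mostly procedural entries.

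What remains is that 5.1.3 lacks a limit to non-serious events and 7.2 lacks an exception for 5.1.3, so the two cannot both be followed as written. The other capture routes hold mainly response data and source notes. They do not supply an adverse event entry with a stated attribution.

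**Conclusion.** The point holds as a conflict between two stated rules. A serious Grade 1 or 2 event clearly due to a procedure is subject to incompatible recording instructions, with no order of precedence. It does not hold as a finding that such SAEs are excluded from reporting, or that the papilloma-swelling signal is lost.

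The airway gap is real but limited. It concerns Grade 1-2 events after dosing that the investigator considers clearly procedural, and what is missing is a record in which that attribution can be reviewed.

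Exposure is about 74 to 120 post-dose EUAs, assuming 37 to 40 treated patients with none omitted, and fewer if accrual stops at stage 1. The number of events affected is unknown, and the percentages above rest wholly on assumed rates. Sample size, alpha, power, the complete response endpoint and the stopping triggers do not change. The correction is worth making because the conflict is plain in the text and costs little to remove.

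**What to change.** Reconcile section 5.1.3 with sections 7.2 and 7.3:

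1. Limit the exclusion in 5.1.3 to non-serious Grade 1 or 2 events clearly due to a procedure.
2. State in 5.1.3 that 7.2 and 7.3 govern all SAEs regardless of grade or attribution, and add a matching cross-reference in 7.2 so that its general documentation rule acknowledges the exception.
3. After the first avelumab dose, record airway adverse events (for example stridor, dyspnea, laryngeal or papilloma edema, airway bleeding) at any grade, with the investigator's attribution noted.

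The cost is a few sentences and some additional low-grade entries, most of them procedural, so reported counts of mild airway events will rise slightly. Noting the attribution lets these be tabulated apart from drug-related events. No visit, procedure, dose or analysis of the primary endpoint changes.

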#### 5.1.4 Collection of Adverse Events during Follow-up

Adverse Events that occur during the follow-up period will only be recorded if they are considered related to the avelumab.

## **5.2 RESPONSE CRITERIA**

Disease stage and response will be determined by flexible nasopharyngolaryngoscopy and/or tracheoscopy using the Derkay staging system if the patient does not have pulmonary disease and/or by imaging if the patient has pulmonary disease [6]. The Derkay staging system has been validated with a high degree of inter-rater reliability [16]. It incorporates an objective score based on the number of sites and bulkiness of papillomas within the pharynx, larynx and trachea and a subjective score determined by voice and breathing symptoms. Physical exam and/or clinic-based endoscopy will be used to visualize all accessible papillomas and assign an objective score using the Derkay system. Only lesions that can be visualized by clinic-based flexible nasopharyngolaryngoscopy and/or tracheoscopy will be included in the baseline score used for assessing treatment response. This score must be 10 or greater for patients to be eligible

for treatment. If patients have disease that is better visualized or only visualized with an imaging study such as CT scan or MRI then imaging studies will be obtained. Preliminary Derkay scores and response assessment will be determined by the endoscopist performing the procedure. Final reporting of clinical responses will be based on a blinded review of endoscopic video and or photos by one or more independent otolaryngologists.

Response and progression from imaging studies will be evaluated in this study using the new international criteria proposed by the revised Response Evaluation Criteria in Solid Tumors (RECIST) guideline (version 1.1) [26]. Changes in the largest diameter (unidimensional measurement) of the tumor lesions are used in the RECIST criteria.

If a subject has disease being assessed by imaging for response and refuses clinic-based flexible nasopharyngolaryngoscopy and/or tracheoscopy, no Derkay score will be calculated. This will not be considered a protocol deviation.

#### 5.2.1 Baseline assessment

- All accessible disease will be examined by physical exam and/or endoscopy to establish a baseline.
- Only lesions visualized by clinic-based flexible nasopharyngolaryngoscopy and/or tracheoscopy will be included in the baseline objective Derkay score.
- Imaging studies will be performed if appropriate and baseline measurements determined using RECIST 1.1 criteria.

#### 5.2.2 Definition of measurable disease

- Any papilloma that can be visualized via clinic-based endoscopy and assigned a score using the Derkay system
- Any papilloma that can be measured by imaging using RECIST 1.1 criteria.

#### 5.2.3 Definition of disease response

##### 5.2.3.1 Complete Remission (CR)

All criteria must be met.

- No evidence of papillomas on physical exam and/or clinic-based flexible nasopharyngolaryngoscopy and/or tracheoscopy.
- No evidence of papillomas by exam under anesthesia (sedation or general anesthesia) with endoscopy and biopsies.
- Absence of disease by imaging if lesions are assessed by imaging.

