## **2 ELIGIBILITY ASSESSMENT AND ENROLLMENT**

### **2.1 ELIGIBILITY CRITERIA**

#### 2.1.1 Inclusion Criteria

##### 2.1.1.1 RRP criteria

- Histological diagnosis of RRP confirmed by pathology report from a CLIA-certified laboratory.
  - One of the following:
    - A Derkey anatomic score of 10 or greater (See Section 12.4) and a history of two or more endoscopic interventions in the last 12 months for control of RRP.
    - Pulmonary RRP with pulmonary disease that is measurable by computed tomography scan.
    - Tracheal involvement with RRP that has required either two or more endoscopic interventions in the last 12 months or a tracheostomy.
  - Greater than or equal to 18 years of age.
- 2.1.1.2 Able to understand and sign the Informed Consent Document.
- 2.1.1.3 Clinical performance status of ECOG 0 or 1. See section 12.1
- 2.1.1.4 Willing to undergo endoscopic evaluation with biopsies in compliance with this protocol.
- 2.1.1.5 No systemic therapy for RRP for four weeks prior to treatment.
- 2.1.1.6 Screening laboratory values must meet the following criteria and should be obtained within 14 days prior to first dose:
- WBC > 2000/ $\mu$ L
  - Neutrophils > 1500/ $\mu$ L
  - Platelets > 100  $\times 10^3$ / $\mu$ L
  - Hemoglobin > 9.0 g/dL
  - Serum creatinine < 1.5 x ULN or creatinine clearance (CrCl) > 30 mL/min (measured or calculated using the Cockcroft-Gault formula below):  
Female CrCl: 
$$\frac{(140 - \text{age in years}) \times \text{weight in kg} \times 0.85}{72 \times \text{serum creatinine in mg/dL}}$$
  
Male CrCl: 
$$\frac{(140 - \text{age in years}) \times \text{weight in kg} \times 1.00}{72 \times \text{serum creatinine in mg/dL}}$$
  - AST/ALT  $\leq$  2.5 x ULN; for subjects with documented metastatic disease to the liver, AST and ALT levels  $\leq$  5 x ULN
  - Total Bilirubin  $\leq$  1.5 x ULN
- 2.1.1.7 Sexually active subjects (men and women) and all subjects of reproductive potential must agree to use two methods of contraception: one highly effective and one other effective method for at least 28 days prior, throughout the avelumab treatment and for at least 60 days after avelumab treatment. Highly Effective Methods are defined as: Intrauterine device (IUD), hormonal (birth control pills, injections, implants), tubal ligation and partner's vasectomy; Other Effective Methods are defined as: latex condom, diaphragm and cervical cap.

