applicable. If patients have a complete response or no response, treatment will be discontinued at that time. If patients have a partial response, treatment will be continued for up to 6 additional weeks (12 weeks total treatment) or until disease progression or complete response. If subjects demonstrate a partial response and receive an additional 6 weeks of treatment their responses will again be measured after completing this additional treatment (+/- 7 days). At the conclusion of treatment all patients will undergo EUA and endoscopy with either standard of care surgical debulking of their disease or biopsies to confirm complete regression of papillomatous disease. The primary endpoint of this study is complete response to treatment, but patients will be followed long-term after completion of treatment to assess timing and frequency of future interventions.

If a patient's condition precludes safe performance of any protocol-driven biopsy, apheresis or other research procedure, the procedure may be delayed for an additional two weeks or canceled at the discretion of the investigator. This will not be considered a protocol deviation. Endoscopy may be omitted in patients with disease that is not endoscopically accessible.

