### 3.3.5 At completion of treatment

- Targeted physical examination if clinically indicated which may include clinic-based flexible nasopharyngolaryngoscopy and/or tracheoscopy
- Vital signs and oxygen saturation at rest and after exertion
- Symptoms of myocarditis (chest pain, shortness of breath, swelling of ankles or feet) will be assessed
- Pregnancy test in women of childbearing potential
- CBC w/differential, LFTs (ALT, AST, total bilirubin, alkaline phosphatase), BUN or serum urea level, creatinine, Ca, Mg, Na, K, Cl, LDH, glucose, amylase, lipase, TSH with reflexive Free T4, Free T3
- TBNK
- Adverse events assessment
- Research blood:
  - 6 CPT tubes (48 mL) will be collected for immunological testing and processed as described in section 4.1.1. Attention [name], [name] contact [contact].
  - 1 SST tube (8 mL) will be obtained for serum collection and processed as described in section 4.1.1 . Attention [name], [name] contact [contact].
- Clinic-based flexible nasopharyngolaryngoscopy and/or tracheoscopy. This will include standard bright light endoscopy and may include videostroboscopy, and assignment of a Derkay score if the Derkay score is being used for response assessment. This endoscopic examination will be used to assess treatment response.
- Imaging studies if imaging is used for response assessment.
- Voice Handicap Index-10 assessment questionnaire.
- Exam under anesthesia (sedation or general anesthesia) including rigid and/or flexible endoscopy with biopsies to perform standard of care papilloma debulking, to obtain biopsies for research and to validate complete response or the presence of persistent disease. These tests will be done 2 and 6 weeks after the first dose of avelumab for all patients. The same tests will be repeated 12 weeks after the first dose for patients that demonstrate a partial response and receive an additional 6 weeks of treatment.

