- A research apheresis sample will be collected prior to first dose of avelumab. Apheresis collection will be 5 L volume (as close to 5 L as possible). Apheresis will only be performed on patients with adequate peripheral venous access. Cells will be transferred to ETIB 's Pre-Clinical Core lab, Attention [name], [name], contact [contact]. Aliquots of PBMC and plasma will be cryopreserved for immunological monitoring. Cell product will be frozen in 10 vials at concentration  $100 \times 10^6$  cells/mL and additional vials at  $300 \times 10^6$  cells/mL. Papilloma and adjacent tissue samples will be collected by biopsy prior to the first dose of avelumab. Biopsies will be obtained with rigid or flexible endoscopy under sedation or general anesthesia. They will consist of up to 10 papilloma fragments, each 1-3 mm in diameter. One fragment may be sent to pathology for permanent sections. The other fragments of the biopsy will be sent to [name] laboratory in sterile 1.5 mL Eppendorf tubes with a small amount of sterile normal saline. Additional tissue that is removed to debulk papillomas may also be collected for research. Up to two fragments of normal mucosa, each 1-3 mm in diameter, will also be obtained and sent to [name] laboratory. Send to [name] lab; [name].

- Patients with papillomas that cannot be biopsied by endoscopy may participate in the trial. All tissue specimen collection except papilloma biopsies will be performed.
- Specimens will be cataloged and stored in ETIB's Pre-Clinical Core lab. Assays will be performed retrospectively.

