## **9 STATISTICAL CONSIDERATIONS**

The trial will be conducted using a Simon optimal two-stage design; the objective is to rule out a 5% complete response rate ( $p_0=0.05$ ) and target a 20% complete response rate ( $p_1=0.20$ ).

The design will use  $\alpha=0.10$  (10% chance of accepting a poor agent) and  $\beta=.10$  (corresponding to 90% power--and 10% chance of incorrectly rejecting a promising agent).

The first stage of accrual will consist of 12 evaluable patients. If 0/12 has a complete clinical response, then no further patients would be enrolled to that cohort. Should 1 or more patients in the first 12 have a complete response, then accrual would continue until a total of 37 evaluable patients have enrolled. If there are 1 to 3 complete responses in 37 patients, this would be considered unacceptably low, while if 4 or more patients have complete responses in 37 patients, then the results will be considered sufficiently promising for further evaluation. Under the null hypothesis (5% complete response rate), the probability of early termination is 54.0%.

It is anticipated that up to 2 patients per month may enroll onto this trial; thus, up to 2 years may be required to complete accrual. The trial would require up to 37 total evaluable patients; the accrual ceiling will be set at 40 patients to allow for a small number of inevaluable patients.

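### Does the complete response definition shut out patients whose disease cannot be reached or biopsied by endoscopy?

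*Combined protocol and SAP*

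**What the plan says.** Section 5.2.3.1 requires every CR criterion to be met. The clinic examination criterion offers alternatives, and the imaging criterion applies only where lesions are assessed by imaging. The criterion for exam under anesthesia (EUA) has no such condition: "No evidence of papillomas by exam under anesthesia (sedation or general anesthesia) with endoscopy and biopsies".

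Eligibility in Section 2.1.1.1 can rest on "Pulmonary RRP with pulmonary disease that is measurable by computed tomography scan". Section 5.2 stages disease and response by endoscopy "and/or by imaging if the patient has pulmonary disease". Section 4.1.1 adds: "Patients with papillomas that cannot be biopsied by endoscopy may participate in the trial".

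Section 3.1.1 states: "At the conclusion of treatment all patients will undergo EUA and endoscopy". Its next paragraph lets a protocol-driven biopsy or other research procedure be delayed or cancelled when the patient's condition makes it unsafe, and closes with: "Endoscopy may be omitted in patients with disease that is not endoscopically accessible".

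Section 9 sets the decision rule: stop if 0 of the first 12 patients have CR; otherwise "accrual would continue until a total of 37 evaluable patients have enrolled", and call the result promising at 4 or more CRs. The accrual ceiling is 40. The term evaluable is not defined.

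**The concern.** Read together, these sections seem to enrol patients for whom one mandatory CR criterion may never be assessed. If the omission sentence in Section 3.1.1 reaches the end-of-treatment EUA, a patient with lung disease only, a clear scan and no EUA cannot be CR. If a biopsy is cancelled or not feasible, a papilloma-free EUA without biopsies fails the criterion too. Section 9 does not say whether such patients stay in the denominator or are replaced.

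CR is the primary endpoint and each decision turns on a single patient: 0 versus 1 of 12, and 3 versus 4 of 37. Losing true CRs would bias the rate downward. In an open-label single-arm trial, settling the reading after scans are known would let results influence the classification. The blinded review in Section 5.2 covers endoscopic video and photographs, so it cannot classify an examination that was not done.

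**Working it through.** **1. Scope of the omission sentence.** Four places favour limiting it to clinic endoscopy.
- Section 2.2.1.3 contains the same sentence, inside the item on clinic-based screening endoscopy.
- Section 3.1.1 requires the final EUA of all patients.
- Section 3.3.5 lists among that EUA's purposes "to validate complete response or the presence of persistent disease".
- Section 11.4.2 says anesthesia and biopsies at completion either confirm CR or accompany debulking.

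For the wider scope there is the sentence's position, at the end of a paragraph on cancelled procedures, and the fact that it does not name the kind of endoscopy. On the narrow scope the CR rule is coherent for lung-only disease: imaging clears the lung and the EUA clears the airway.

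**2. Biopsies.** The sentence in Section 4.1.1 that follows the one quoted excuses papilloma biopsies only; other tissue collection continues, and that section includes normal mucosa among the samples. It concerns collection before treatment and sets no rule for confirming CR. The cancellation clause in Section 3.1.1 applies only where the procedure is unsafe and is framed around research procedures, whereas the same section gives end-of-treatment biopsies a response purpose. Whether the clause reaches them is arguable.

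**3. Default classification.** A patient lacking a required criterion is not CR. Sections 5.2.3.2 to 5.2.3.4 then place the patient in partial response, progression or, as the remainder, stable disease. Partial response needs no EUA.

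**4. The plan's own figures.** Inputs from Section 9: n1 = 12, stop at 0; n = 37, promising at 4 or more; p0 = 0.05, p1 = 0.20.

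P(promising) = Σ over x = 1 to 12 of P(X1 = x) × P(X2 ≥ 4 − x), with X1 ~ Bin(12, p) and X2 ~ Bin(25, p).

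- At p = 0.05: 0.0935, within the 0.10 limit. Early stop 0.95^12 = 0.540, matching the stated 54.0%.
- At p = 0.20: terms for x = 1, 2, 3 are 0.1859, 0.2757 and 0.2353; x ≥ 4 adds 0.2054. Sum 0.902. False early stop 0.8^12 = 0.069.

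**5. Size if affected patients count as non-CR.** Assume a share q is affected and would otherwise respond at the same rate. Replace p by p(1 − q). Expected CRs lost in 37 are 37 × 0.20 × q.

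| q (assumed) | CRs lost | Power | False stop at 0/12 | Type I error |
|---|---|---|---|---|
| 0 | 0 | 90.2% | 6.9% | 9.3% |
| 5% | 0.37 | 88.2% | 8.0% | 8.1% |
| 10% | 0.74 | 85.7% | 9.2% | 6.9% |
| 20% | 1.48 | 79.2% | 12.3% | 4.9% |

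In patient counts, one affected patient in the first 12 gives power 88.2% and a false stop of 0.8^11 = 8.6%. One more among the next 25 gives power 87.6%.

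**6. Size if affected patients are replaced.** With K ~ Bin(40, q) affected, evaluable n = min(37, 40 − K), and the cut-off stays at 4. Power is 90.1%, 89.4% or 86.2% for q = 5%, 10% or 20%. The ceiling absorbs 40 − 37 = 3 such patients at no cost.

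**7. Size of the risk in relaxing the rule.** Suppose CR could rest on imaging alone in some patients and their CR rate under the null were 10% instead of 5% (an assumption). With a 10% share, p = 0.9 × 0.05 + 0.1 × 0.10 = 0.055 and type I error is 12.1%. With a 20% share, p = 0.8 × 0.05 + 0.2 × 0.10 = 0.060 and it is 15.1%.

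**The case for a change.** The strongest case for a change is that the literal default, though usable, may not be intended. Nothing in the plan says that patients admitted on lung disease alone, or with papillomas that cannot be biopsied, should be unable to reach the primary endpoint. The wording is asymmetric too: imaging is conditional and the EUA is not. One sentence, written before responses are known, would remove the doubt at little cost.

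Part of this stands. Section 3.1.1 does not state the scope of its omission sentence, and Section 9 leaves evaluable undefined. A papilloma-free EUA without biopsies is classified only by reading the criterion strictly. The risk of deciding late is also real in principle.

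It does not carry the point further. To be affected, a patient must have disease that is inaccessible or not biopsied, must actually miss the EUA or the biopsies, and must otherwise have cleared completely. The documents give no figure for how often that happens. The substantive remedy, CR by imaging alone, goes beyond clarification. It weakens confirmation of the primary endpoint, and because Section 3.1.1 stops treatment on CR and continues it on partial response, it could alter who stays on treatment.

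**Conclusion.** No change to the plan is needed. What is missing is the scope of one sentence and the meaning of evaluable. An analyst can fill both sensibly: keep the EUA for all patients as Section 3.1.1 requires, treat a missing criterion as non-CR, and report the number of such patients.

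On the better-supported reading, with biopsies done, the loss is zero. Otherwise the effect is conservative. For assumed shares of 5% to 20%, power at a 20% CR rate is 88.2% to 79.2% if these patients count as non-CR, or 90.1% to 86.2% if they are replaced up to the ceiling, against 90.2% as designed. Type I error is not inflated. These figures rest on assumed shares and on affected patients responding at the same rate as the others; the documents support no particular value.

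Requiring direct examination under anesthesia before declaring CR is a fair trade-off. It may miss an occasional true CR and it guards against false ones. Relaxing it offers an uncertain gain in power against a possible rise in type I error to 12.1% or 15.1%, under the assumed null rates shown.
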